5.4.3 Focused Ultrasound Procedure

The focused ultrasound exposure will be performed using the Haifu® Model-JC200 Focused Ultrasound Tumour Therapeutic System at the Churchill Hospital site.

The acoustic window identified in the Ultrasound Session (section 5.1.3.1) is recreated with the participant in position and under anaesthetic. Slice by slice therapy then follows: the tumour volume consists of several two-dimensional cross-sectional 'slices', and the shape and size of the tumour within each slice will naturally vary. In this way, the radiologically accessible tumour volume is divided into sequential slices, at 2-10 mm intervals depending on the therapeutic plan as shown in Figure 6. In therapy mode, the tumour volume is treated with focused ultrasound to attempt to attain regional hyperthermia in the tumour for duration of at least 30 minutes and ideally 60-90 minutes.

[figure not shown]

Figure 6: Schematic representation of the row-by-row, slice-by-slice approach used to induce mild hyperthermia into the target tumour volume using a stop/start single-shot mode treatment plan. Moving beam (linear mode) is also under investigation for hyperthermia using the same approach.

5.4.4 Passive Acoustic Monitoring

FUS exposure will be monitored using B-mode diagnostic Ultrasound that is incorporated into the HIFU therapeutic device. During exposure, a prototype Passive Cavitation Detector will optionally be used to simultaneously passively monitor ultrasonic emissions from the targeted tumour area. This prototype has previously been demonstrated during a previous study, to not interfere with FUS exposures using the JC200.

5.4.5 Participant Monitoring

All participants will be monitored continuously while under General Anaesthetic and throughout the intervention. The anaesthetic team (anaesthetist and ODP) will perform this monitoring according to standard protocols for HIFU.

6 EARLY PATIENT WITHDRAWAL

Withdrawal

During the course of the trial, a patient may withdraw early from completing the trial. This may happen for a number of reasons, including:

- Unacceptable toxicity
- AE/SAEs requiring discontinuation
- Clinical decision
- Patient decision

Possible reasons for a clinical decision to remove a participant from the study include, but are not limited to:

- New exclusion criteria including new pregnancy
- Significant protocol deviation or non-compliance with the protocol

Patient withdrawals must be documented in the eCRF. SAEs must be followed until resolution. The reason for withdrawing from treatment early should be clearly documented in the medical records.

Consent Withdrawal

A patient may withdraw consent from study participation (Consent withdrawal) at any time for any reason. Every effort should be made to ascertain the reason for withdrawal and this should be documented in the medical records. The trial office must be informed via completion of the Consent Withdrawal eCRF. Under these conditions, investigators are still responsible to follow up any SAEs till resolution.

For data collection purposes, subjects are considered as completing the study if they have died during the study, are lost to follow-up, or withdraw consent.

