Primary Endpoint:	A demonstrable two-fold increase in, or value exceeding 10µg/g of, the concentration of intra-tumoural doxorubicin at the treated tumour site following FUS-induced mild hyperthermia, in at least 50% of evaluable participants.
Secondary Endpoints:	
 Part I only: Achievement of the desired range of mild hyperthermia in the target tissue as monitored by the implanted thermometry device during FUS exposure

	
 2. Persistence of cell viability stain or percentage of cell or tissue necrosis under 30% following FUS exposure, as assessed by cytological or histological methods 3. Significant bone marrow suppression, deranged liver function and liver toxicity. 4. Adverse events up to 30 days post-intervention: 
 a. Deemed related to ThermoDox® b. Deemed related to FUS
Tertiary (Exploratory) Endpoints:	
Regarding doxorubicin released by optimal FUS exposure parameters:
 
 1. Combined analysis of relevant end points to establish most effective alternative analytical method(s) for quantifying drug release: 
 a. Released biopsy samples exhibiting averaged regions of nuclear or background fluorescence levels at least twice that of a suitable control, as assessed by fluorescence microscopy b. Liver MRI/MR-Spectroscopy indicating targeted delivery of doxorubicin to the tumour by demonstrating a statistically significant increase in the tumour:background ratio of signal intensity following intervention compared to baseline c. A significant decrease of in total doxorubicin plasma levels over time-matched clearance levels, following FUS-induced release 2. Radiological evidence of tumour response at timepoints up to 60 days post-intervention in the FUS-targeted tumour and control(s), as assessed by Principles of Choi and RECIST response evaluation using MRI and CT [11, 12] and SUV_{max} using PET-CT [13]

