4.1 Eligibility criteria for entry into the main study

The Investigator will determine patient eligibility based on the following inclusion/exclusion criteria.

4.1.1 Inclusion criteria:

Patients will only be eligible for inclusion in this study if all of the following criteria apply:

1. Pathologically confirmed advanced solid tumour with liver metastasis suitable for intervention (as assessed by ultrasound or other radiological methods). In addition confirmed primary liver tumours (hepatocellular carcinoma or cholangiocarcinoma) can be included.
2. Will have progressed or remained stable on conventional chemotherapy.
3. Male or Female, Age ≥ 18 years.
4. Have life expectancy of ≥ 3 months.
5. Left Ventricular Ejection Fraction (LVEF) $\geq 50\%$ on echocardiogram.
6. Have not received radiotherapy to the target area within the preceding 12 months.
7. A World Health Organisation (WHO) performance status of ≤ 1 (Appendix 1).
8. Able and willing to give written informed consent, indicating that they are aware of the investigational nature of this study and potential risks, and able to comply with the protocol for the duration of the study, including scheduled follow-up visits and examinations.

4.1.2 Exclusion criteria:

Patients will be ineligible for recruitment to the study if any of the following conditions hold:

1. Have surgery or other procedure requiring general anaesthesia planned to be undertaken during the period of the study.
2. Have serious illnesses including, but not limited to, congestive heart failure (NYHA class III or IV functional classification); life threatening cardiac arrhythmia; or myocardial infarction or cerebral vascular accident within the last 6 months.
3. Have on going significant infection (chest, urine, blood, intra-abdominal).
4. Have uncontrolled diabetes.
5. Have received a life-time dose of doxorubicin $> 450 \text{ mg/m}^2$ or a life-time dose of epirubicin $> 900 \text{ mg/m}^2$ or any dose of both.
6. Pregnant or breast-feeding. In women of childbearing potential, a negative pregnancy test (serum) is required within 30 days prior to study intervention.

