7. Female participants of child bearing potential and male participants whose partner is of child bearing potential who are not willing to practice an acceptable form of contraception (i.e. oral contraceptive, diaphragm, cervical cap, condom, surgical sterility) during the study and for 6 months thereafter. Women whose partner has or men who have undergone a vasectomy must use a second form of birth control.
8. Have any known allergic reactions to any of the drugs or liposomal components or intravenous imaging agents to be used in this study.
9. Have portal or hepatic vein tumour invasion/thrombosis.
10. Inadequate Haematological and Biochemical indices:

Lab Test	Exclude if:
INR	> 1.5 times the institution's upper normal limit (UNL)*
Absolute neutrophil count	$< 1,500/\text{mm}^3$ (or $< 1.5 (10^9/\text{L})$)
Platelet count	$< 60,000/\text{mm}^3$ (or $< 60 (10^9/\text{L})$)
Hgb	$< 9.0 \text{ g/dL}^{**}$
Serum creatinine, or Calculated creatinine clearance (CrCl)	$\geq 2.5 \text{ mg/dL}$ (or $\geq 221 \mu\text{mol/L}$) $\leq 25.0 \text{ mL/min.}$
Serum bilirubin	$> 3.0 \text{ mg/dL}$ (or $> 51 \mu\text{mol/L}$)

Serum albumin	< 2.8 g/dL (or <28 g/L)
---------------	-------------------------

* Except in patients who are therapeutically anticoagulated for medical conditions unrelated to cancer such as atrial fibrillation. Subjects may be re-screened after the condition is treated or anticoagulant is withheld

** Unless the haemoglobin value has been stable, the patient is cardiovascularly stable, asymptomatic, and judged to withstand the FUS procedure

11. Have contraindications to receiving doxorubicin including prior sensitivity (rash, dyspnoea, wheezing, urticarial or other symptoms) attributed to anthracyclines or other liposomal drugs.
12. Use of chemotherapy or of an investigational drug within 30 days or 5 half-lives, whichever is longer, preceding the intervention.
13. Have medically significant active infection.
14. Have Child-Pugh Class C liver disease, or Class A-B with encephalopathy and/or refractory ascites (Appendix 3).
15. Documented HIV positive.
16. Documented diagnosis of haemochromatosis.
17. Documented history of contrast-induced nephropathy.
18. Have any of the following contraindications for liver biopsy:
 - a. Suspected liver haemangioma or other vascular tumour
 - b. Tense ascites
 - c. Known cystic liver disease*
 - d. Extra-hepatic biliary obstruction*

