8.3 Duration of treatment

One day only; participants should receive a single iv infusion of ThermoDox® at a dose of 50mg/m² on the day of the intervention in accordance with specific timing as dictated by the team administering the intervention. No further doses are required or should be given as part of this study in either Part I or II. A participant having a dose of ThermoDox® in Part I is not eligible for re-entry into Part II for any further dose.

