13.4 Expected adverse events

Appendix 2 of the current approved ThermoDox[®] IB [44] lists all the adverse events associated with the use of ThermoDox[®] in clinical studies. ThermoDox[®] contains Adriamycin[®] (doxorubicin) as its active chemotherapy agent and ThermoDox[®] has a similar toxicity profile to doxorubicin. Appendix 1 of the current approved ThermoDox[®] IB [44] lists all the adverse events known to be associated with the use of doxorubicin. A copy of this document must be held in the Site File for reference.

Please note much of the adverse event data for ThermoDox[®] has been obtained from a global, randomized Phase III study (HEAT) which involves combining ThermoDox[®] with RFA in the treatment of hepatic tumours, in patients with inoperable hepatocellular carcinoma (HCC). Adding 50mg/m² of ThermoDox[®] to RFA was found to be safe with an adverse event profile similar to that of the single agent doxorubicin. However given the difference in patient population, it is possible that in this study population other side effects may occur, or the patient might suffer a more severe reaction.

As per ThermoDox[®] IB amendment version date 11th October 2013 (the current approved ThermoDox[®] IB at the time of the initial trial approval), grade 3+ neutropenia and leucopenia were the only¹⁹ SAEs occurring in over 5% of HEAT Study patients and were not seen in the arm receiving RFA without ThermoDox[®] (Table 7). The detailed and current list of SAEs and AEs in 701 patients for this study, can be found in Appendix 2 of the current approved ThermoDox[®] IB

¹⁹ The only other grade 3+ adverse events affecting at least 5% of subjects were elevations in liver enzymes which is an expected occurrence in the patient group used for the HEAT study (hepatocellular carcinoma). The RFA alone vs RFA+ThermoDox[®] study arms did not differ significantly in this respect.

[44]. Further details regarding the frequency of AEs and SAEs in patients treated with ThermoDox® using targeted application of heat by RFA or microwave have been included in a recent publication [10].

Adverse Event	RFA Alone N=347		RFA+ThermoDox® N=354		p-value
	N	%	N	%	
Neutropenia	0	0	65	18.9	<0.0001
Leukopenia	0	0.0	21	6.1	<0.0001

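### Section 6 allows removal after the single dose for newly met exclusion criteria, some of which are the toxicity being measured, and follow-up after removal is stated inconsistently

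*Protocol*

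**What the plan says.** Section 6 introduces its list with "Possible reasons for a clinical decision to remove a participant from the study include, but are not limited to". The two grounds named are "New exclusion criteria including new pregnancy" and "Significant protocol deviation or non-compliance with the protocol". Neither is tied to the time before or after dosing.

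Section 8.3 fixes treatment as a single infusion on the intervention day: "No further doses are required or should be given as part of this study in either Part I or II".

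Exclusion item 10 in section 4.1.2, headed "Inadequate Haematological and Biochemical indices", sets limits for neutrophils, platelets, haemoglobin, bilirubin, albumin, creatinine and INR. Items 3 and 13 exclude infection. A secondary endpoint is "Significant bone marrow suppression, deranged liver function and liver toxicity", which Table 2 reads from Grade 3 and 4 laboratory results at Day 1 and Day 15.

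Three places govern what happens after withdrawal:
- Section 5.3 (closing paragraph): adverse events are recorded for 30 days after the intervention, and nothing else is required.
- Section 13.9: where an adverse event requires discontinuation from the study, laboratory tests are repeated at least weekly until the event resolves or stabilises.
- Section 18.5: a patient who withdraws is followed up according to the protocol.

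**The concern.** In a trial with repeated dosing, newly meeting an exclusion criterion can be a reason to stop further treatment. Here nothing remains to be stopped after Day 1, so removal from the study only ends data collection. A low neutrophil count or an infection after ThermoDox can be a harm the trial is there to count, and under section 6 it is also a permitted reason to stop observing that participant.

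If the permission were used, scheduled bloods and scans would be missing more often in participants with toxicity. Later laboratory data and the radiological response endpoint would then lean towards those who tolerated the drug better. With at most 28 evaluable participants (section 16.1), a few such losses matter. They would not be made good, because section 6.1 replaces only patients who are not evaluable for the primary endpoint.

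A protocol deviation is not a toxicity, and nothing in the text links it to the outcome. It belongs here only because, after a single dose, it is likewise no reason to lose planned data.

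**Working it through.** **Which data can be lost.** Set against the schedule, section 5.3 affects the endpoints as follows.

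- Primary endpoint: Table 1 uses biopsy material processed within 12 hours of the intervention. It is fixed before later toxicity can lead to removal. Not affected.
- Laboratory toxicity endpoint: the scheduled post-dose bloods are on Days 2, 15 and 30, and Table 2 uses nothing later than Day 15. A neutropenia first seen at the Day 15 draw is already captured. Exposed only for a participant removed before that draw.
- Day 30 bloods: exposed for anyone removed earlier. They show recovery or a later abnormality.
- Radiological response: Table 3 reads this exploratory endpoint from scans up to Day 60 and attaches the qualifier that it be shown in at least 50% of evaluable participants. The 4-week scans are exposed, and so is the flexible set (Day 12 to 60) if not yet done.

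**How many could become removable.** The plan gives no figure to reproduce. Inputs:
- Table 7 (section 13.4): 65 patients with neutropenia on RFA plus ThermoDox, column N = 354. The text there says "grade 3+ neutropenia and leucopenia were the only" serious events above 5%.
- Maximum of 28 evaluable participants (section 16.1).
- Assumption: Grade 3+ neutropenia lies below the item 10 limit of 1,500/mm³.

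Rate: 65/354 = 18.4%. Table 7 prints 18.9%, which matches a denominator of 344 (65/344 = 18.9%). The difference is immaterial here.

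Expected number: 28 × 0.184 = 5.1 (28 × 0.189 = 5.3).

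With X binomial (28, 0.184): P(X ≥ 1) = 0.997 and P(X ≥ 3) = 0.91 (0.92 at the printed 18.9%).

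These figures count participants to whom section 6 could be applied on this one ground. They do not predict removals.

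**What it would do to the response endpoint.** Suppose k of 28 are removed before any response scan and r of the remaining 28 − k respond. The proportion among all 28 lies between r/28 (none of the k would have responded) and (r + k)/28 (all would have).

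- k = 5, r = 12: observed 12/23 = 52%; bounds 12/28 = 43% and 17/28 = 61%.
- k = 3, r = 13: observed 13/25 = 52%; bounds 13/28 = 46% and 16/28 = 57%.

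Both intervals contain 50%, so in either case the missing participants could decide whether the qualifier is met.

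**The case against.** The strongest reply is that section 6 only lists possible reasons for a clinical decision, and that much survives removal. Adverse events are still recorded for 30 days, serious events are followed to resolution or stabilisation, and section 13.2 makes every Grade 4 laboratory abnormality a serious event. Section 13.9 adds weekly tests, and section 17.1 keeps all patients evaluable for toxicity. Section 6 must also cover the weeks before dosing, where a newly met exclusion criterion is an ordinary reason to stop. Finally, section 12 says follow-up imaging is not essential to the success of the study.

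Most of this stands, and it rules out several stronger readings that a reader might infer:
- That the primary result is at risk. It rests on Day 1 tissue.
- That 5 of 28 would be removed. Removal is discretionary, and the rate comes from an RFA population that section 13.4 itself says differs from this one.
- That no analysis could help. The trigger is often a recorded blood value, so an analysis can condition on it or give bounds as above. Going further than bounds needs assumptions that the data cannot test.
- That all exclusion criteria are toxicities. Many, such as HIV status, contraception and haemochromatosis, are not.

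The reply does not close the gap. The weekly tests apply only where an adverse event requires discontinuation, and they include no scans. Section 18.5 either leads back to section 5.3 or contradicts it. Section 17.1 also sets apart patients who do not complete the required safety observations.

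**Conclusion.** The point holds in a limited form. As written, a participant can be removed after dosing because of an outcome under study, and section 5.3 then releases the site from the remaining scheduled bloods and scans, while sections 13.9 and 18.5 say something different.

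The exposure is Day 15 bloods for those removed before that draw, Day 30 bloods, and the scans behind one exploratory endpoint. About 5 of 28 is an upper illustration for Grade 3+ neutropenia. It rests on the Table 7 rate carrying over, on such events falling below the item 10 limit, and on every such participant being removed. The 43% to 61% range further assumes that all 5 leave before any response scan. The flexible scan may be done from Day 12, so some response data could already exist.

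It would go too far to conclude that toxicity should never lead to withdrawal. Section 6 lists unacceptable toxicity as a reason in its own right, and that clinical judgement is not in question here. The issue is whether planned data collection continues.

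**What to change.** Add to section 6 that, once the ThermoDox infusion has started, newly met exclusion criteria and protocol deviations are recorded but do not by themselves end scheduled follow-up. The planned Day 2, 15 and 30 bloods and the follow-up scans continue unless the participant withdraws consent or the investigator omits a procedure on clinical grounds, with the reason recorded. Data collected in this way stay in the analyses. The wording for the period before the infusion can remain, and clinical decisions on toxicity stay with the investigator.

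Reconcile sections 5.3, 13.9 and 18.5 with this text, so that the protocol gives one account of what is collected after withdrawal.

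Cost: a few sentences by amendment, and visits for participants who would otherwise have left. Those visits are already in the schedule. The sample size does not change.

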6.1 Patient evaluability and replacement

Patients who are not evaluable for the primary endpoint will be replaced.

7 SAMPLES FOR LABORATORY ANALYSIS

7.1 Samples to be analysed in local Trust's laboratories

7.1.1 Diagnostic Laboratories

Samples for haematology, biochemistry and coagulation analysis will be labelled with unique study patient identifiers and sent to the local hospital diagnostic laboratory. Results will be processed in the standard way and entered into the routine hospital reporting system. Samples will be stored, held, reported and subsequently destroyed in accordance with standard local laboratory practice.

7.1.2 Pathology

No pathology samples are required for pathological analysis in the Trust during any part of the study period, although in the evaluation of histological sections of biopsy tissue, the opinion of an NHS pathologist may be sought.

7.2 Samples to be sent to and analysed in a Central Laboratory

The following samples will be analysed at the Oxford Cancer Research Centre:

- Pharmacokinetic blood samples to measure Unreleased and Released plasma levels of doxorubicin, using Pre-Treatment Plasma as the control
- Biopsy samples to quantify intra-tumoural uptake of doxorubicin (three in Part I, up to two in Part II)

Details of sample preparation, labelling and despatch are provided in the TARDOX Sample Handling Manual.

7.3 Pharmacokinetic assays

Plasma samples will be used to quantify the levels of doxorubicin as per the time points in section 5.5.3. The infusion start & stop times, duration of FUS exposure and sample collection times during intervention will be recorded.

7.4 Pharmacodynamic assays

Not applicable to this study.

7.5 Summary of samples/assays to be taken during the study

Assay/sample handling and storage will be managed according to separate written instructions. The following summarises the arrangements for collection, close to patient handling, timings, and analytical laboratories responsible. Research assays will be performed according to separate laboratory SOPs.

7.6 Samples for Biobanking

Participants in this trial will be invited to permit the long term retention of samples left over after protocol-specified analyses for use in possible other future research linked to trial data. Consent to participate in this aspect of the trial is optional and not a requirement of participation in the main study.

7.7 Labelling and confidentiality of samples sent

All samples sent to analytical Laboratories will be labelled with the trial code, trial patient number, and the date & time taken. Should a laboratory receive any samples carrying patient identifiable information the recipient must immediately obliterate this information and re-label. The study site will be informed of their error.

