Study Design:	
Phase 1 prospective non-randomised safety cohort study with all patients recruited from a single UK site (Oxford). The study has an open label design with all participants receiving ThermoDox® and FUS. The study will run in two parts. Part I is required to identify optimal FUS exposure parameters using real time thermometry data from an implanted thermometry device, such as a thermistor. Part II does not require implantation of thermometry device and is designed to more accurately reflect how the therapy would be implemented in clinical practice. All evaluable participants from both Part I and Part II will be included in the endpoint analysis.
 
Part I
 
For each participant, a single liver tumour will receive the intervention and follow-up imaging. The ability to achieve targeted release of doxorubicin from ThermoDox® at the tumour site will be determined using three tumour biopsies with corresponding peripheral blood samples taken during intervention and/or using a radiological method (MR-Spectroscopy).
 
Part II
 
For each participant, a single liver tumour will receive the intervention and follow-up imaging.. The optimal FUS exposure parameters determined in Part I will be selected for Part II interventions, accounting for differences in propagation path length identified in the Ultrasound Session. The ability to achieve targeted release of doxorubicin from ThermoDox® at the tumour site will be determined using the same methods as for Part I, with the exception of requiring only two tumour biopsies.
 
In the 30 days following intervention, both Part I and II participants will be followed up with a maximum of two CTs, two PET-CTs and three MRI/MR-Spectroscopy scans. There is however built in flexibility for the scans to be performed at different timepoints up to 60 days post intervention should the patient provide this optional consent and not have started another treatment. If available, other non-FUS control tumour(s) in the liver exposed to ThermoDox® alone will be selected as controls against which radiological response in the FUS-targeted tumour (target tumour) will be compared.
 
Detailed criteria for evaluation of efficacy and safety are described in subsequent sections.

Patient Numbers:	A maximum of 28 evaluable participants will be recruited to the study overall.

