¹⁰ During the Ultrasound Session feasibility of intervention is confirmed and a target tumour will be selected by ultrasound. Only one screening ultrasound is required.

¹¹ MRI includes the abdomen. Measurements made using the modified RECIST 1.1 criteria.

¹² Liver MRI includes the abdomen. The first Liver MRI/MR Spectroscopy following intervention can alternatively be performed on the same day as intervention, if intervention is in the morning. It should occur within 36 hours of the completion of intervention, and ideally within 24 hours where possible.

¹³ Liver pCT includes the abdomen. Measurements made using CHOI and the modified RECIST 1.1 criteria.

¹⁴ Three blood samples for pharmacokinetics in both Phases I and II (Pre-Treatment, Unreleased drug, Released drug).

¹⁵ Three biopsies in Part I (Pre-Treatment, Unreleased drug, Released drug), two biopsies in Part II (Released drug).

KEY DEFINITIONS

“Intervention” refers to attempted targeted release of ThermoDox® by mild hyperthermia using a focused ultrasound.

The “FUS-targeted tumour” or “target tumour” refers to the liver tumour treated with FUS following ThermoDox® delivery. This is in contrast to the RECIST definition, which defines target tumours as those measurable lesions which are followed through the patient’s treatment course.

A “non-FUS control tumour” refers to a liver tumour receiving ThermoDox® alone which has been selected for radiological follow-up and comparison with the target tumour.

The “desired range of mild hyperthermia” is used in the context of ThermoDox® release in this study and is defined as achieved bulk tissue temperature in the range of 41-47°C

“Optimal FUS exposure parameters” are defined as those combinations of settings on the HIFU device (power, duty cycle and transducer motion plan) which result in an adequate temperature rise to successfully release doxorubicin from the LTSls in the target tumour, without causing direct thermal tissue damage.

An “evaluable participant” is defined as a participant who has received FUS following delivery of ThermoDox® in Part I or II, and for whom it has been possible to evaluate the outcome of the intervention based on biopsy samples, or radiologically.

An “evaluable sample” is defined as a sample for which sufficient material was available for analysis and the analytical technique has provided quantifiable data.

ABBREVIATIONS

AE	Adverse Event
ADL	Activities of Daily Living
ADR	Adverse Drug Reaction

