To assess the safety of FUS-induced mild hyperthermia for drug delivery	1. Persistence of cell viability stain or percentage of cell or tissue necrosis under 30% following FUS exposure, as assessed by cytological or histological	1. Cytological or histological analysis of biopsy samples processed within 96hr of intervention†

	methods ¹⁶ ‡,§ 2. Adverse events deemed related to FUS up to 30 days post-intervention	2. Adverse event recording for 30 days post-intervention
To assess the local and systemic cytotoxic effects of ThermoDox® in this setting	1. Significant bone marrow suppression, deranged liver function and liver toxicity 2. Adverse events deemed related to ThermoDox® up to 30 days post-intervention	1. Grade 3 and 4 laboratory results from blood tests at Day 1 and Day 15 post intervention 2. Adverse event recording for 30 days post-intervention

Table 2: Secondary Objectives and Endpoints for Parts I & II of the TARDOX Study

Regarding participants for which doxorubicin has been released by optimal FUS exposure parameters:

Tertiary (Exploratory) Objectives	Tertiary (Exploratory) Endpoints	How and when data is captured
1. To establish the validity of other minimally-invasive and non-invasive methods of evaluating intratumoural uptake of doxorubicin as an alternative to that used in primary endpoint	Combined analysis of relevant end points to establish most effective alternative analytical method(s) for quantifying drug release	See below
a. Fluorescence microscopy of biopsy	Released biopsy samples exhibiting regions of nuclear or background fluorescence levels at least twice that of a suitable control, as assessed by fluorescence microscopy ‡,§	Microscopic analysis of biopsy samples processed within 96hr of intervention†
b. MR-Spectroscopy	Liver MRI/MR-Spectroscopy indicating ¹⁷ targeted delivery of doxorubicin to the tumour by demonstrating a statistically significant increase in the tumour:background ratio of signal intensity following intervention compared to baseline	MRI/MR-Spectroscopy signal within 36 hours of intervention
c. Plasma pharmacokinetics	A statistically significant decrease in total doxorubicin plasma levels over time-matched clearance levels, following HIFU-induced release	Analytical chemistry of plasma samples processed within 12hr of intervention†

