12.1 Measurement of disease for solid tumour

Objective disease response in the target tumour and the non-FUS control tumours, if any, will be independently measured according to the principles of Choi and RECIST response evaluation using MRI and CT [11, 12] and SUV_{max} using PET-CT [13]. In both Part I and Part II, radiological tumour response with CT and MRI scans will be evaluated prior to study entry and following intervention as per the follow-up schedule (section 2.3). Response classification will be used in the analysis of trial data.

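### The protocol provides for no masked reading of the reader-judged secondary and exploratory endpoints, although coded slides and numbered lesions would be cheap to add

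*Protocol*

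**What the plan says.** **Design.** The synopsis states: "The study has an open label design with all participants receiving ThermoDox® and FUS". Footnote 15 to the schedule of events lists the cores: "Three biopsies in Part I (Pre-Treatment, Unreleased drug, Released drug), two biopsies in Part II (Released drug"). Section 5.4.2 fixes the order in which the Part I cores are taken.

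**Labels.** Section 7.7 applies one rule to every laboratory sample: "All samples sent to analytical Laboratories will be labelled with the trial code, trial patient number, and the date & time taken". Further detail is deferred. Section 7.2 says "Details of sample preparation, labelling and despatch are provided in the TARDOX Sample Handling Manual", and section 7.5 says "Research assays will be performed according to separate laboratory SOPs".

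**Judged endpoints.**
- Table 2 (secondary): "Persistence of cell viability stain or percentage of cell or tissue necrosis under 30% following FUS exposure, as assessed by cytological or histological" methods. Footnote 16 allows an alternative where baseline necrosis is high: an increase of no more than 25% over a suitable control.
- Table 3, item 1a (exploratory): "Released biopsy samples exhibiting regions of nuclear or background fluorescence levels at least twice that of a suitable control". The synopsis version of this endpoint refers to averaged regions; Table 3 omits the averaging.
- Table 3, item 2 (exploratory): radiological response in the FUS-targeted tumour and any controls. Section 12.1 says of the target tumour and the controls that "the non-FUS control tumours, if any, will be independently measured", using the principles of Choi and RECIST on MRI and CT and SUVmax on PET-CT.

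All three carry the § mark in section 3, so each must be shown in at least half of evaluable participants.

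**The concern.** Percentage necrosis, persistence of a stain, the choice of fluorescent regions and the placing of measurements on a tumour all leave room for judgement. A reader who knows that a core came after FUS, or which lesion was heated, may lean without intending to towards the result the team hopes for. In a single-arm, open-label trial the comparison of cores or lesions within a participant carries much of the interpretive weight, and masking the reader is a simple way to protect it.

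At stake are the tissue-level evidence that FUS was not ablative, one of the alternative measures of drug delivery, and the exploratory signal of tumour response.

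**Working it through.** The plan states no figure on this point, so the check sets the provisions side by side.

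**1. Can core type be inferred?** The label does not carry it. In Part I there are three core types in a fixed sequence, so sorting one participant's labels by time identifies each core. In Part II every core is Released, so there is no other core type within the participant to tell apart. The label therefore matters for Part I.

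**2. Does anything else hide it?** No section mentions blinding, masking, recoding or reading order for histology, cytology, fluorescence or imaging. Section 7.1.2 says only that a pathologist's opinion may be sought, so no separate histology reader is fixed. The control is left as a suitable one, without definition, in both Table 3 item 1a and footnote 16, which widens discretion.

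**3. Does section 12.1 mask the imaging?** Independent measurement most naturally means that target and control lesions are each measured separately. It does not say that the reader is unaware of which lesion had FUS.

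**4. Which endpoints are exposed?**

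| Endpoint | Method | Exposed? |
|---|---|---|
| Primary: intra-tumoural doxorubicin | Analytical chemistry on a recorded mass (Table 1) | No |
| Secondary: viability or necrosis | Reader; absolute 30% cut, or footnote 16 against a control | Yes |
| Exploratory 1a: fluorescence regions | Reader; ratio to a control | Yes |
| Exploratory 1c: plasma levels | Analytical chemistry | No |
| Exploratory 2: tumour size or density | Reader; target versus control lesions | Yes, where a control exists |
| Exploratory 2: SUVmax | Maximum uptake in a region | Less so |

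**5. How sensitive is the 50% rule?** This shows the rule's behaviour and does not estimate bias. Section 16.1 caps evaluable participants at 28, so the rule needs 14, and one reclassified participant moves the proportion by 1/28 = 3.6 percentage points. Assume a true success rate p, and that a share f of true failures is read as success with no error the other way. The apparent rate is q = p + f(1 − p), and the chance of meeting the rule is P(X ≥ 14) for X ~ Binomial(28, q).

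| p | f = 0 | f = 0.05 | f = 0.10 | f = 0.20 |
|---|---|---|---|---|
| 0.30 | 0.021 | 0.052 | 0.111 | 0.325 |
| 0.40 | 0.187 | 0.287 | 0.405 | 0.656 |

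Both p and f are assumptions with no source in the protocol. Twenty-eight is also the most favourable number, because microscopy and histology are done only where tissue mass allows.

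**The case against.** Four points can be made on the other side.

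- **Masking may be set elsewhere.** A reader might infer that no reader is masked. The documents do not show that. The Sample Handling Manual and the laboratory SOPs are not at hand and could hold recoding rules. What stands is that the protocol provides for none, and that imaging is not a sample-handling matter.
- **The label has a purpose.** A reader might infer that section 7.7 is itself an error. It is a traceability and confidentiality rule, and collection times are needed (sections 5.4.2 and 7.3). The gap is the lack of any recoding before reading.
- **Not everything is judged by eye.** A reader might infer that all the secondary tissue and exploratory comparisons are visual, and that masking is the only bias control. Plasma levels are chemistry, the main necrosis rule is an absolute cut, response follows Choi and RECIST principles with identical imaging techniques (section 12.2), and the primary endpoint is assay-based. An absolute cut still needs a reading, so knowing that a core is Released can still matter.
- **Size.** The wording of Table 3 might suggest that a reader could pick the brightest fields and so carry a result past 50%. The synopsis refers to averaged regions, and the documents give no field variability, ratio distribution or reader error from which to calculate such an effect.

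The stakes are also limited. At most one technique beyond the primary assay is expected per sample (section 3), and section 12 calls follow-up imaging not essential to the study's success.

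**Conclusion.** The point holds in a limited form. The protocol makes no provision for masked reading of one secondary endpoint (viability or necrosis) and two exploratory ones (fluorescence regions, and tumour size or density against control lesions). In Part I the label times together with the fixed core order let a reader infer core type, and section 12.1 does not conceal which tumour had FUS. The primary endpoint and plasma pharmacokinetics are untouched.

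Neither the direction nor the size of any bias can be derived from the documents. The conclusion rests on the protocol alone and would weaken for the tissue readings if the unseen manual or SOPs already require recoding. This is a cheap improvement and not a flaw that threatens the trial's main conclusion.

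**What to change.** **Tissue (sections 7.2 and 7.7).** Keep collection times in the trial log. Before reading, give microscopy and histology samples a random code, with the key held away from the reader. Read Part I cores in random order, mixed with Part II cores. Place fields by a fixed rule and average them, and bring Table 3 into line with the synopsis on averaging. Labels for plasma and for the primary assay need not change.

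**Imaging (section 12.1).** Where a control lesion exists, give the existing radiology reader numbered lesions without FUS status, and open the key only after the measurements are locked.

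**Cost.** A code list and a reading order, with the same readers, samples and participants, and slightly more handling. Two limits remain: a needle track may reveal the treated lesion on some scans, and a participant with no control lesion (section 12.2.1 allows for this) cannot be masked. The change has to precede the readings, since masking cannot be restored to a reading already made.
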